5.4 Subject Disposition

The number of subjects in each analysis population will be presented along with reason for any exclusions. Subject accountability will be summarized by visit. The number of subjects who are enrolled, eligible for follow-up, and number completing clinical follow-up will be summarized for each protocol-required visit. In addition, the number of subjects who complete the study or exit early will be summarized by reason.

Sta	atistical Analysis Plan	Page	9 of 14
Sponsor	Study		Version
ACUTUS Medical	AcQBlate Force Sensing Ablation System US IDE/EU Study for Atrial Flutter (AcQForce Flutter & AcQForce Flutter-EU)		2.0

5.5 Demographics and Baseline Characteristics

Demographics, baseline data, including but not limited to relevant descriptors from the medical history, co-morbidities, and medications, will be summarized.

Procedural data collection will also be analyzed and summarized.

5.6 Analysis of Study Endpoints

5.6.1 Primary Safety Endpoint

The primary safety endpoint is defined as the proportion of mITT and select ITT Failure subjects (i.e., subjects who had the AcQBlate FORCE Catheter inserted) who are free from a composite list of pre-specified device/procedure related SAEs that occur through 7-days post ablation procedure. Subjects who do not have evidence of a SAE/SADE from the composite list of safety events will be considered a success.

Serious adverse events that meet the definition for Primary Safety Endpoint are pre-defined and include:

- Death
- Cardiac tamponade/perforation
- Myocardial infarction
- Stroke
- Systemic embolism
- Major access site complications
- Major bleeding requiring transfusion
- Complete heart block
- Other SAEs/SADEs adjudicated by an independent review as "probably or definitely related" to the Investigational device.

5.6.1.1 Primary Safety Endpoint Analysis

The null and alternate hypotheses for primary safety endpoint are as follows:

Sta	atistical Analysis Plan	Page	10 of 14
Sponsor	Study		Version
ACUTUS Medical	AcQBlate Force Sensing Ablation System US IDE/EU Study for Atrial Flutter (AcQForce Flutter & AcQForce Flutter-EU)		2.0

Ho: The proportion of mITT subjects and select ITT Failure subjects (ρ) who are free from device/procedure related SAE through 7-days post ablation procedure is less than or equal to 93.0%.

Ho: $\rho \leq 93.0\%$

Ha: The proportion of mITT and select ITT Failure subjects (ρ)who are free from device/procedure related SAE through 7-days post ablation procedure is greater than 93.0%.

Ha: ρ > 93.0%

The null hypothesis will be rejected if the one-sided 95% Clopper-Pearson Exact lower confidence bound is greater than 93.0%.

5.6.1.2 Sensitivity Analysis

Sensitivity analyses to assess the effect of missing data on the primary safety endpoint will be performed including:

• A tipping point analysis in which missing data are varied from worst case to best case to evaluate mITT and ITT Failure subjects with missing primary safety data.

5.6.2 Primary Efficacy Endpoint

The primary efficacy endpoint is defined as the proportion of mITT subjects (β) achieving acute procedural success. Acute procedural success is defined as the demonstration of bidirectional cavotricuspid isthmus block confirmed at least 20 minutes following the last radiofrequency (RF) application at the cavotricuspid isthmus with the investigational catheter.

5.6.2.1 Primary Efficacy Endpoint Analysis

The null and alternate hypotheses for primary efficacy endpoint are as follows:

Ho: The proportion of mITT subjects (β) demonstrating bidirectional cavotricuspid isthmus block confirmed at 20 minutes following the last right atrial radiofrequency (RF) application at the cavotricuspid isthmus with the investigational catheter is less than or equal to 83.7%.

St	atistical Analysis Plan	Page	11 of 14
Sponsor	Study		Version
ACUTUS Medical	AcQBlate Force Sensing Ablation System US IDE/EU Study for Atrial Flutter (AcQForce Flutter & AcQForce Flutter-EU)		2.0

Ho: β ≤ 83.7%

Ha: The proportion of mITT subjects (β) demonstrating bidirectional cavotricuspid isthmus block confirmed at 20 minutes following the last right atrial radiofrequency (RF) application at the cavotricuspid isthmus with the investigational catheter is greater than 83.7%.

Ha: β > 83.7%

The null hypothesis will be rejected if the one-sided 95% Clopper-Pearson Exact lower confidence bound is greater than 83.7%.

A primary efficacy failure will comprise the following:

- The inability to achieve and maintain bidirectional CTI block at least 20 minutes following the last RF application with the investigation device. A second investigative catheter or alternate AcQBlate FORCE catheter curve may be used prior to designation as failure. Maximum RF time before considering a non-investigational catheter is at the discretion of the Investigator but shall not exceed 60 minutes of RF time. OR
- The use of a commercially available non-investigational catheter for any ablation of the CTI.

NOTE: Use of isoproterenol is at the discretion of the Investigator.

5.6.2.2 Sensitivity Analysis

Sensitivity analyses to assess the effect of missing data on the primary efficacy endpoint will be performed including:

• A tipping point analysis in which missing data are varied from worst case to best case to evaluate subjects with missing primary efficacy data in the mITT analysis set.

5.6.3 Other Safety Analyses

Adverse events (AE) will be reported for all mITT and ITT Failure subjects.

Sta	atistical Analysis Plan	Page	12 of 14
Sponsor	Study		Version
ACUTUS Medical	AcQBlate Force Sensing Ablation System US IDE/EU Study for Atrial Flutter (AcQForce Flutter & AcQForce Flutter-EU)		2.0

Individual device/procedure related SAEs at 7-days will be analyzed by event frequencies and proportions of subjects. Total and individual non-serious, device/procedure related AEs at 30-days will also be analyzed by event frequencies and proportion of subjects. Adverse events will be analyzed in terms of their severity, action taken, and duration to resolution.

Device Deficiency Reports will be analyzed for frequencies of safety events and proportion of subjects as part of the safety analyses.

All AEs and SAEs will be tabulated with the number of events and subjects with event for each event type and overall. The rate of all AEs and SAEs reported in the study will be reported as well as the rates at 7 and 30 days. AEs and SAEs will also be summarized by relatedness and severity. Adverse events leading to death or study discontinuation will be provided in listing format. Rates will be reported as the number of subjects who experience at least one event during the analysis interval out of the total number of subjects with follow-up to the beginning of the analysis interval.

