11.5 Subject Study Completion and Withdrawal

Subject participation will be considered concluded when the 1-month visit is completed, and all data collection is complete. Subjects who withdraw for any reason will have all available data entered into the EDC. Reasons for withdrawal will be entered on the Study Exit eCRF.

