5.1.1 Descriptive Statistics

Continuous variables will be summarized as means, standard deviations, medians, and ranges. Categorical variables will be summarized as frequencies and percentages.

Confidence intervals may be presented, where appropriate, using the t-distribution for continuous data and Clopper-Pearson Exact method for categorical variables.

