5.1.2 Study Day

Study day 0 is the date of the index procedure. Day in study will be calculated relative to the index procedure as follows:

Study Day = Assessment Date – Index Procedure Date

For each subject, duration in study will be based on last study contact date which is the latest date of all follow-up visits, assessments, adverse event onset or resolution, and study exit including date of death.

Statistical Analysis Plan Page			7 of 14
Sponsor	Study		Version
ACUTUS Medical	AcQBlate Force Sensing Ablation System US IDE/EU Study for Atrial Flutter (AcQForce Flutter & AcQForce Flutter-EU)		2.0

Duration variables will be calculated as follows:

Duration Days = End Date – Start Date

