5.2 Analysis Populations

The following analysis populations are defined for analysis:

- 1. The **Enrolled Analysis Set** will consist of subjects who have signed an informed consent form, are deemed study eligible by meeting all of the inclusion and none of the exclusion criteria up to the point of the procedure.
- 2. The **Pre-procedure Testing (PPT) Failure Set** will consist of enrolled subjects who have presented for the procedure in any rhythm other than sinus rhythm or typical atrial flutter and have not undergone venous access. These subjects will be treated per the recommendations of the study physician and exited from the study. No use of the investigational device is allowed. A Study Exit electronic case report form (eCRF) will be completed.
- 3. The Intention-to-Treat (ITT) Failure Analysis Set will consist of enrolled subjects who have the venous access portion of the ablation procedure initiated, regardless of whether the AcQBlate FORCE Catheter has been inserted, and up to the point of completion of the right-atrial access but prior to any RF application with the

S	tatistical Analysis Plan	Page	8 of 14
Sponsor	Study		Version
ACUTUS Medical	AcQBlate Force Sensing Ablation System US IDE/EU Study for Atrial Flutter (AcQForce Flutter & AcQForce Flutter-EU)		2.0

investigational device. The ITT Failure subjects will be followed for safety reasons through the 7-day follow-up visit. All ITT Failure subjects will be excluded from any efficacy data analysis. In addition to the Discharge eCRF and the 7-day Follow-up eCRF, a Study Exit eCRF will also be completed. The ITT Failure population may include:

- At the time of the procedure, if the subject does not demonstrate conduction through cavotricuspid isthmus, the subject will be exited from the study and followed for safety through the 7-day follow-up visit.
- At the time of procedure, if atrial fibrillation is initiated during the process of inducing typical AFL, a direct current cardioversion (DCCV) may be performed to attempt conversion to sinus rhythm so that the CTI conduction portion of the study may proceed. If during confirmation of the CTI conduction, the investigator determines that further ablation beyond the CTI is warranted the subject will be exited from the study and followed for safety through the 7-day follow-up visit.

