5.3 Handling of Missing Data

All attempts will be made to limit the amount of missing data. Unless otherwise specified, no attempt will be made to impute missing data. If a data point is missing, that data point will not contribute to that portion of the analysis. The number of evaluable observations will be reported in analysis so that extent of missing data can be assessed. Sensitivity analyses will be performed for the primary safety and efficacy endpoints as detailed in Section 6.6.

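### The adverse event duration-to-resolution summary in SAP 5.6.3 covers resolved events only, so reported durations are biased short

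*Combined protocol and SAP*

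**What the plan says.** SAP 5.6.3, repeating protocol 8.2.2, states: "Adverse events will be analyzed in terms of their severity, action taken, and duration to resolution". It names no estimator for duration. The rules that would apply are the general ones:

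- SAP 5.1.2, for duration variables: "Duration Days = End Date – Start Date".
- SAP 5.1.1: "Continuous variables will be summarized as means, standard deviations, medians, and ranges".
- SAP 5.3: "Unless otherwise specified, no attempt will be made to impute missing data", and "If a data point is missing, that data point will not contribute to that portion of the analysis".

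No section gives a censoring rule, a substitute end date or an ongoing-at-exit category for adverse event duration. SAP 5.1.2 defines a last study contact date but uses it only for duration in study.

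Follow-up is short. For mITT subjects it ends around day 30 (30 ± 7 days, protocol 7.9.2); protocol 11.5 says: "Subject participation will be considered concluded when the 1-month visit is completed, and all data collection is complete". For the others, SAP 5.2 says: "The ITT Failure subjects will be followed for safety reasons through the 7-day follow-up visit". Protocol 9.1 goes further for serious events only: reports continue until the event subsides or, with permanent impairment, until it stabilises.

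**The concern.** An event still open when the subject leaves the study has no end date, so the end-minus-start duration cannot be computed. Under SAP 5.3 it then contributes nothing to the duration summary, which describes only events that resolved while someone was watching. The chance of being included falls as duration rises, so the summary leans toward short events.

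Two groups are most exposed. For non-serious events, no follow-up past the last scheduled visit is stated. Permanent impairments that stabilise never acquire a resolution date, even with the extended reporting in protocol 9.1. The risk list in protocol 10.1 includes femoral nerve injury, phrenic nerve damage and diaphragmatic paralysis, which could outlast a 30-day window.

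At stake is a descriptive safety table in a submission meant to support a PMA application. A reader could take a mean of about two weeks as the typical time to recovery when it partly reflects the length of follow-up.

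**Working it through.** **Plan's own figure.** There is none to reproduce. The documents give no expected duration, no expected proportion unresolved and no adverse event duration distribution.

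**Direction.** Let T be the true duration and C the time from onset to last contact. Under the rules above, T enters the summary only if T ≤ C. If C does not depend on T, the probability of inclusion at T = t is P(C ≥ t), which cannot rise as t rises. Longer events therefore get equal or lower weight, and the bias is downward or nil.

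**Size, as an illustration.** Inputs:
- Exit at day 30 for mITT subjects (protocol 7.9.2) and day 7 for ITT Failure subjects (SAP 5.2).
- Assumed: exponential durations with mean m from 3 to 60 days.
- Assumed: onset at day 0, so C equals the exit day c.

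With q = exp(−c/m), the fraction dropped is q and the reported mean is m − c·q/(1 − q).

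Worked case, m = 30 and c = 30: q = exp(−1) = 0.368. Reported mean = 30 − 30 × 0.368/0.632 = 12.5 days.

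| True mean (days) | Dropped, exit day 30 | Reported mean, exit day 30 | Reported mean, exit day 7 |
|---|---|---|---|
| 3 | 0.0% | 3.0 | 2.3 |
| 7 | 1.4% | 6.6 | 2.9 |
| 14 | 11.7% | 10.0 | 3.2 |
| 30 | 36.8% | 12.5 | 3.4 |
| 60 | 60.7% | 13.8 | 3.4 |

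Simulation with 1,000,000 draws per case agrees with the formula.

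**Does the median rescue it?** The SAP also reports medians. With day-30 exit and day-0 onset, the median among resolved events is 4.8 days against a true 4.9 (m = 7), 8.2 against 9.7 (m = 14), 11.4 against 20.8 (m = 30) and 13.1 against 41.6 (m = 60). It shows the same pattern.

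**Sensitivity to onset and exit.** With onset uniform over 30 days, the reported means for m = 3, 7, 14, 30 and 60 are 2.7, 5.0, 7.0, 8.4 and 9.2 days, with 10%, 23%, 41%, 63% and 79% dropped. At the late edge of the visit window (exit day 37, onset day 0), m = 30 gives 14.8 days and m = 60 gives 16.6 days.

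**Which events are dropped?** With uniform onset and day-30 exit, 15% to 37% of dropped events are shorter than the true median. A late start alone can leave a short event open.

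**The case against.** The strongest reply is that the rule is pieced together. A general duration formula and a general missing-data default are joined, and neither mentions ongoing events. The SAP never says that an event known to be continuing counts as a missing data point. Protocol 9 also lists duration as an item recorded on the Adverse Event eCRF, so the derivation might not be used at all. This is fair as far as it goes. But SAP 5.1.2 states its formula for duration variables without exception, no other rule tells the programmer what to do, and an event still open has no final duration on the eCRF either.

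A reader might infer that persistent harms disappear from the safety report. The documents do not support that. SAP 5.6.3 tabulates all adverse events and SAEs, with summaries by relatedness and severity, and SAP 5.3 adds: "The number of evaluable observations will be reported in analysis so that extent of missing data can be assessed". Outcome is recorded on the eCRF (protocol 9), and source notes must track continuation or resolution (protocol 11.8). These safeguards limit the effect without removing it. The evaluable number does not separate an ongoing event from an unrecorded date. SAP 5.6.3 promises no outcome table. Its adverse event listings cover only events leading to death or discontinuation, and SAP section 7 names no others.

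A reader might also infer that SAEs as a class are affected, or that the dropped events are always the longest. Neither holds. Protocol 9.1 should give most SAEs an end date after exit, leaving mainly impairments that only stabilise. Being the longest is a tendency, as the uniform-onset result shows.

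Finally, a Kaplan-Meier estimate has its own limits. Several events in one subject are not independent, and some groups will be tiny: at the 3% expected event rate in protocol 3.2, 110 subjects give 0.03 × 110 ≈ 3 primary safety events. This stands, and it is why the unresolved count comes first in the fix.

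**Conclusion.** The point holds as a minor one. Followed as written, the SAP produces a duration summary restricted to resolved events, and that summary is biased short. The bias is negligible if events typically last a few days (nil at a 3-day mean and −0.4 day at 7 days with day-30 exit). It reaches −4.0 days at a 14-day mean and about −17 days at 30. Between true means of 30 and 60 days the reported mean moves only from 12.5 to 13.8, so the summary barely separates moderately long from persistent events.

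The sizes rest on assumed exponential durations and onset at day 0; the documents supply neither. The direction needs only that time under observation does not depend on duration, and that an ongoing event is handled as one without an end date. The analysis is descriptive. It plays no part in the success criteria (protocol 8.4) or the sample size (protocol 8.8).

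**What to change.** Amend SAP 5.6.3 as follows:

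1. Beside any duration summary, report the number and percentage of events unresolved at last contact, counted separately from events whose end date was simply not recorded.
2. Label the end-minus-start summary as resolved events only.
3. Where event numbers allow, add a Kaplan-Meier median time to resolution, censoring unresolved events at the last study contact date already defined in SAP 5.1.2. Do not count death as resolution. State that a median may not be reached: in the 60-day illustration the true median of 41.6 days lies beyond a day-30 exit.
4. Make any confidence interval allow for several events in one subject.

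Start date, outcome and last contact date are already collected or derived, so no new data are needed. The cost is a few lines of SAP text and minor programming. No primary endpoint, sample size or success criterion changes.

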7.6 CTI Ablation Procedure

7.6.1 Confirmation of Conduction through the CTI

Entrainment pacing from the cavotricuspid isthmus during atrial flutter will be attempted prior to initiating RF ablation to verify that the CTI is part of the arrhythmia circuit. When clinically reasonable, the investigator may attempt to induce atrial flutter using pacing maneuvers when the subject presents to the lab in sinus rhythm.

Documentation of concealed entrainment should be printed and recorded on the appropriate eCRF.

If Investigator is unable to induce and entrain CTI dependent AFL, the Investigator may choose to confirm and document conduction through the CTI. CTI conduction must be confirmed prior to initiating RF ablation. Documentation of inability to induce and/or entrain should be printed and recorded on the appropriate eCRF. Confirmation of conduction through the CTI should be demonstrated using pacing maneuvers.

Documentation of conduction through the CTI should be printed and recorded on appropriate CRF.

If CTI dependent AFL cannot be confirmed or CTI conduction cannot be confirmed, the subject will be considered an ITT failure subject and exited from the study at the 7-day follow-up visit.

If during inducement, entrainment, or other pacing maneuvers the subject is paced into AF, DCCV may be performed to attempt conversion to sinus rhythm so the CTI conduction measurement may proceed. If the investigator determines further ablation beyond the CTI is warranted the subject will be exited from the study after being followed for 7-days for safety.

The AcQBlate FORCE catheter shall not be used to initiate ablation procedure until conduction through the CTI is confirmed.

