- 4. The Modified Intention-to-Treat (mITT) Analysis Set will consist of enrolled subjects who initiates the ablation procedure using the AcQBlate Force Sensing System. An initiated ablation procedure is defined as a procedure where the AcQBlate Force Sensing System is used for the ablation procedure irrespective if a non-investigational device was used to complete the ablations. mITT subjects will be followed for all study outcome measures for the full duration of the clinical study and will comprise the data set for the Primary Efficacy Endpoints.

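### SAP 5.6.3 leaves the 30-day adverse event interval undefined; if it starts at day 0, and in any case for the whole-study rate, subjects who exit by design at the 7-day visit dilute the rate

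*Combined protocol and SAP*

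**What the plan says.** Four statements in the SAP and one in the protocol bear on this.

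- **Population.** SAP 5.6.3: "Adverse events (AE) will be reported for all mITT and ITT Failure subjects".
- **Rate.** In SAP 5.6.3 the numerator is the "number of subjects who experience at least one event during the analysis interval". For the denominator, the condition looks only at where the interval starts: "out of the total number of subjects with follow-up to the beginning of the analysis interval".
- **Time points.** SAP 5.6.3: "The rate of all AEs and SAEs reported in the study will be reported as well as the rates at 7 and 30 days". Non-serious "device/procedure related AEs at 30-days will also be analyzed by event frequencies and proportion of subjects". No interval bounds are given for either.
- **Follow-up.** SAP 5.2: "The ITT Failure subjects will be followed for safety reasons through the 7-day follow-up visit". For the treated set, by contrast, "mITT subjects will be followed for all study outcome measures for the full duration of the clinical study".
- **Exit.** Protocol 7.6.1 says that when neither CTI-dependent flutter nor CTI conduction can be confirmed, "the subject will be considered an ITT failure subject and exited from the study at the 7-day follow-up visit".

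Neither document adds an end-of-interval requirement, a censoring rule or an mITT-only 30-day AE rate.

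**The concern.** A denominator fixed at the start of an interval is sound when everyone in it is followed to the end, or when the rate allows for those who are not. Here one of the two groups in the AE set is taken off study at about one week by design. When a rate runs from the procedure to day 30 or to study end, each such subject without an early event counts as event-free for a period in which nobody was looking. mITT subjects lost before day 30 are handled in the same way.

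The consequence is an AE or SAE rate that is somewhat too low in data meant to support a PMA. The undefined interval is a second problem: two programmers could follow SAP 5.6.3 faithfully and produce different 30-day tables.

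**Working it through.** The documents state no 30-day AE rate and no expected number of ITT Failures, so there is no plan figure to reproduce. The check is direct arithmetic.

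**Inputs from the documents**
- N, mITT subjects: 110 (minimum) to 120 (maximum), protocol 8.8.
- Day 0 is the index procedure, SAP 5.1.2.
- ITT Failures exit at the 7-day visit, which protocol 7.9.1 sets at 7 ± 3 days after discharge.

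**Assumptions, not in the documents**
- k, ITT Failures: 2, 5, 10 or 20.
- a, AE risk in days 0-7, and b, AE risk in days 8-30 among those event-free at day 7. The pairs (a, b) tried are (5%, 2%), (10%, 5%), (10%, 10%) and (20%, 10%).
- The same risks apply in both groups, which isolates the effect of lost follow-up. Exit is at day 7.

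**Interval of days 0-30**

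Rate with everyone followed to day 30: a + (1-a)b.

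Rate under the SAP rule: [N(a + (1-a)b) + k·a]/(N+k). ITT Failure events up to exit do count; only those after exit are lost.

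Difference: -k(1-a)b/(N+k).

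Example with N = 110, k = 10, a = 10%, b = 5%:
- full follow-up: 0.10 + 0.90 × 0.05 = 14.50%
- shortfall: 10 × 0.90 × 0.05/120 = 0.375 points
- SAP rule: 14.13%

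Results for N = 110 under the SAP rule:

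| a, b | Full follow-up | k = 2 | k = 5 | k = 10 | k = 20 |
|---|---|---|---|---|---|
| 5%, 2% | 6.90% | 6.87% | 6.82% | 6.74% | 6.61% |
| 10%, 5% | 14.50% | 14.42% | 14.30% | 14.13% | 13.81% |
| 10%, 10% | 19.00% | 18.84% | 18.61% | 18.25% | 17.62% |
| 20%, 10% | 28.00% | 27.86% | 27.65% | 27.33% | 26.77% |

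With N = 120 the differences are the same or slightly smaller. Across all these combinations the shortfall is 0.03 to 1.38 points, or 0.5% to 7.3% in relative terms. The four pairs do not include a = 5% with b = 10%. There, with N = 110 and k = 20, the shortfall is 20 × 0.95 × 0.10/130 = 1.46 points, so the upper end is near 1.4 to 1.5.

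**Whole-study rate.** This runs from the procedure whichever way the 30-day interval is defined. The same formula applies, with b read as the risk from exit to study end.

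**Interval of days 8-30**

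Subjects who exited by day 7 are not under follow-up when the interval begins, so the quoted rule itself removes them. The rate is N·b/N = b, with no dilution. A residue remains if the 7-day call, and so the exit, falls after day 7. In the worst case with N = 110, k = 10 and b = 5%, all ten are counted at the start and contribute no event: 110 × 0.05/120 = 4.58% instead of 5.00%.

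**The case against.** The strongest reply is that the SAP does not say the 30-day interval starts at day 0. A condition about follow-up to the beginning of an interval does little work if every interval begins at the procedure, so a second interval of days 8-30 is plausible, and it removes nearly all the dilution. This stands as far as it goes, and it means the 30-day rate cannot be called too low without qualification. It does not dispose of the point. Rates at 7 and 30 days read most naturally as two cumulative figures from one origin, the whole-study rate starts at day 0 regardless, and a days 8-30 table would leave no cumulative 30-day rate.

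Two stronger inferences are tempting and not supported.

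- **That the bias always favours the device.** The lost-follow-up part can only lower a day-0 rate. The net effect of including ITT Failures, compared with the mITT rate, also depends on their own early events. These subjects have venous access and may be cardioverted; if their event proportion exceeded the mITT 30-day rate, including them would raise the figure. In the other direction, if they had no events at all, the gap from the mITT rate would be 0.11 to 4.31 points over the same combinations. Most of that gap would reflect lower risk, not lost observation.
- **That nothing after day 7 can be seen in them.** The call is timed from discharge with a window of 3 days either side, so some are observed beyond post-procedure day 7.

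It is also fair to say that a reader could partly see the problem in planned outputs: evaluable counts (SAP 5.3), subjects completing each visit (SAP 5.4) and subjects with events (SAP 5.6.3). That aids transparency but neither defines the interval nor corrects the rate.

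**Conclusion.** The point holds in limited form. SAP 5.6.3 is wrong as written for the whole-study rate, and for the 30-day rate if its interval starts at day 0. If the interval is days 8-30, the 30-day rate is close to right, and the fault is mainly that the SAP does not say so.

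The size is small: about 0.03 to 1.4 percentage points under the assumed k, a and b, and material only if ITT Failures are numerous. Only mITT enrolment is capped, so the documents set no limit on k. They also disagree on who counts. Protocol 6.7 keeps ITT subjects without catheter insertion out of every safety analysis, while SAP 5.6.3 includes all ITT Failures in AE reporting. That choice changes k and must be reconciled.

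A reader might infer that the main safety conclusion is at risk. It is not. The primary safety endpoint is assessed through 7 days in mITT and catheter-inserted ITT Failure subjects against 93.0% (SAP 5.6.1 and 5.6.1.1), and study success (protocol 8.4) does not use the rates discussed here.

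**What to change.** In SAP 5.6.3:

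1. State the interval bounds: days 0-7 and days 0-30, both from the index procedure.
2. Report 30-day and whole-study AE and SAE rates in mITT subjects as Kaplan-Meier estimates with exit as censoring. Alternatively, give crude rates with the number followed to the end of the interval beside them.
3. Report ITT Failure AEs separately, through their exit at the 7-day visit.
4. Keep the combined set for the 7-day rate.

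Two tempting alternatives are weaker. Restricting the denominator to subjects with an event or followed to day 23 (the lower edge of the 30 ± 7 day window) drops event-free early exits and biases the rate upward. Suppose, as an assumption, 110 mITT subjects with 6 first events by day 7 and 12 later, a true rate of 18/110 = 16.4%. If 10 event-free subjects are lost just after day 7, that rule gives (6 + 94 × 12/104)/100 = 16.8%. Kaplan-Meier on the combined set would assign the late risk of treated subjects to subjects who never received RF.

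The cost is a few words in the SAP, a small programming change and one extra table row. The downside for the sponsor is a slightly less favourable 30-day rate.
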